4.9. Analysis Plans

Patients' demographic information, laboratory test results and concomitant medications, including neoadjuvant chemotherapy at baseline will be analyzed, with data summarized in tables listing the distributions of the variables along with the number of subjects per treatment arm in order to assess comparability. Patients' information on post-operative shoulder pain, nausea, vomiting, intubation and measures from Postoperative Morbidity Survey will be collected. The Fisher's exact test or Chi-square test will be applied to assess the association between two categorical variables. We will summarize the distribution of average and cumulative intraoperative insufflation pressure, Post Anesthesia discharge DASAIM scores, length of ICU and hospital stay by each treatment. We will use the student t-test or the Wilcoxon rank sum test to compare continuous variables between two different patient groups. Logistic regression will be utilized to assess the effects of patient prognostic factors, comorbidities and treatment on postoperative shoulder pain and postoperative morbidity.

Adverse event (AE) data will be summarized by frequency tables. The association between the types and severity of AE and the treatment will be evaluated.

5. Study Drug Information

Since both Sugammadex and Neostigmine are FDA approved, Insert recommendations and Institutional Standards will be followed for all study agents.

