4.2.2 Cumulative intraoperative insufflation pressure (mmHg min) during the surgery

4.2.3 Subjective grading of quality of surgical exposure expressed by surgeon at end of case using Surgical Rating Scale (Martini, Boon, Bevers, Aarts, & Dahan, 2013)

4.2.4 Readiness to discharge from the Post-Anesthesia Care Unit (PACU) as determined by a modified version of the Dansk Selskab for Anæstesiologi og Intensiv Medicin (DASAIM) discharge criteria scoring system to be completed at 15, 45 and 90 minutes after admission to the PACU

4.2.5 Degree of Post-Operative Nausea and Vomiting (PONV) per Visual Analog Scale and number of episodes of emesis per nurse in PACU

4.2.6 Length of Intensive Care Unit (ICU) & Hospital stay, 30-Day Mortality and Readmission Rate

4.2.7 Measures of organ dysfunction and perfusion by the Postoperative Morbidity Survey (De novo need for oxygen supplementation, ability to tolerate an enteral diet, oliguria or Acute Kidney Injury, Delirium or new neurological deficits) and postoperative lactate

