6.2.4. Postoperative Pain: A Survey will be completed by the PACU nurse. The patient will be asked if INCISIONAL, VISCERAL and/or SHOULDER PAIN are present. The nurse will record Visual Analog Scale (VAS) pain score (1-10) for pain in general and for Shoulder Pain if present, recording these separately. All these will be recorded at 15, 45 and 90 minutes (if patient not previously discharged). Opioids administered by the PACU nurse will be measured in morphine equivalents.

6.2.5. Readiness to Discharge from PACU: Readiness to discharge from the PACU as determined by a modified version of the DASAIM discharge criteria scoring system (Gartner, Callesen, Kroman, & Kehlet, 2010) (Phillips, Street, Kent, Haesler, & Cadeddu, 2013) to be completed at 15, 45 and 90 minutes (if patient not previously discharged) after admission to the PACU. A patient will be considered ready for discharge if cumulative score is 4 or less and no single category has a score greater than 1.

DASAIM Discharge Criteria Scoring System (Gartner, Callesen, Kroman, & Kehlet, 2010)		
Sedation	0	Patient is fully awake
(Nurse Evaluation)	1	Patient is asleep, aroused by verbal stimulation
	2	Patient is asleep, aroused by physical stimulation
	3	Patient is asleep, cannot be aroused
Respiratory Rate	0	Respiratory rate > 10
(Nurse count)	1	Snoring, 10 < RR <30
	2	RR < 10 or RR > 30/min
	3	Periods of apnea or obstructive patterns
Oxygen Saturation	0	SpO2 ≥ 94%
(No supplemental oxygen for 10 minutes)	1	90% ≤ SpO2 < 94%
	2	85% ≤ SpO2 < 90%
	3	SpO2 < 85%

Systolic Blood Pressure	0	SBP \geq 100mmHg
	1	90mmHg \leq SBP < 100mmHg
	2	80mmHg \leq SBP < 90mmHg or SBP > 220mmHg
	3	SBP < 80mmHg
Heart Rate	0	50 < HR \leq 100
	1	100 < HR \leq 120
	2	40 < HR \leq 50 or 120 < HR \leq 130
	3	HR < 40 or HR > 130
Pain at rest	0	No pain
(Patient evaluation)	1	Light pain
	2	Moderate pain
	3	Severe pain
Nausea	0	No nausea or vomiting
	1	Light nausea or vomiting without previous nausea
	2	Moderate nausea and/or vomiting
	3	Severe nausea and/or vomiting

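### DASAIM is scored at 45 and 90 minutes only in patients still in the PACU, and section 4.9 has no rule for those already discharged, so later comparisons of readiness are selected on the outcome itself

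*Combined protocol and SAP*

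**What the plan says.** Section 4.2.4 names readiness to leave the PACU as the outcome, judged by a modified DASAIM "discharge criteria scoring system to be completed at 15, 45 and 90 minutes after admission to the PACU". It serves hypothesis 2.1, which expects deep block to bring a faster recovery.

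Section 6.2.5 adds a condition that 4.2.4 and the synopsis do not carry. The scoring is "to be completed at 15, 45 and 90 minutes (if patient not previously discharged) after admission to the PACU". It also supplies a yes/no rule: "A patient will be considered ready for discharge if cumulative score is 4 or less and no single category has a score greater than 1".

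Section 4.9 promises this for DASAIM: "We will summarize the distribution of average and cumulative intraoperative insufflation pressure, Post Anesthesia discharge DASAIM scores, length of ICU and hospital stay by each" arm. The next sentence reads: "We will use the student t-test or the Wilcoxon rank sum test to compare continuous variables between two different patient groups". Earlier in the same section, for categorical data: "The Fisher's exact test or Chi-square test will be applied to assess the association between two categorical variables". Section 4.9 does not mention the 6.2.5 rule, a DASAIM time point, or the value to be used for a patient who has already left the PACU.

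**The concern.** Leaving the PACU is close to being the outcome. A comparison of 45- or 90-minute scores among patients still present therefore conditions on an event after randomisation that the treatment is expected to change. If deep block with Sugammadex does speed recovery, that arm loses more of its best patients from the later comparisons. Those who remain are the slow recoverers of each arm, and randomisation no longer makes them comparable.

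At stake is the interpretation of one secondary outcome. A true gain in recovery could be missed, and the later score differences would not estimate the effect on readiness among the patients randomised.

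**Working it through.** **1. Inputs from the documents.** Scoring times and the not-discharged condition (6.2.5); readiness rule (6.2.5); tests (4.9); 48 per group (4.8). The documents give no PACU stay, DASAIM distribution, readiness rate or expected effect on recovery. Every DASAIM figure below rests on assumed inputs.

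**2. The plan's own figure.** The only power stated is for the primary outcome: 88% with 48 per group, 60% v 28.6%, two-sided 0.05, chi-square. The mean proportion is (0.60 + 0.286)/2 = 0.443.

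z = [√48 × 0.314 − 1.96 × √(2 × 0.443 × 0.557)] / √(0.60 × 0.40 + 0.286 × 0.714) = (2.175 − 1.377)/0.666 = 1.198

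This gives 88.5% power. Also 96/(1 − 0.04) = 100. Both reproduce, and this point does not touch them.

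**3. Model A: who is left to score.** Seven correlated DASAIM items scored 0–3, 48 per arm, 3,000 replicates per scenario, 6.2.5 rule applied. Assumed true readiness by 15, 45 and 90 minutes is 32, 58 and 79% with moderate block and 54, 78 and 92% with deep block. If every ready patient leaves before the next assessment, those scored at 45 minutes are 100 − 32 = 68% v 100 − 54 = 46%. At 90 minutes the simulated shares are 42% v 23%, or about 0.42 × 48 = 20 v 0.23 × 48 = 11 patients.

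**4. Model A: power.** Power is for a result favouring deep block, with Wilcoxon applied to scored patients only. The comparator is a rank test on the first assessment at which the patient is ready (15, 45, 90, not by 90), in all patients. It has about 67% power whatever the departure rate.

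| Ready patients who leave | 45 min | minus 67 | 90 min | minus 67 |
|---|---|---|---|---|
| 0% | 76% | +9 | 66% | −1 |
| 25% | 69% | +2 | 56% | −11 |
| 50% | 61% | −6 | 42% | −25 |
| 75% | 47% | −20 | 23% | −44 |
| 100% | 27% | −40 | 12% | −55 |

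**5. Model B: a different structure.** Lognormal time to readiness (log-SD 0.5), median 25% shorter with deep block, control median 45 to 120 minutes, score falling with time relative to readiness, 48 per arm, 1,000 runs per scenario. Ranges are over the control medians.

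| Ready patients who leave | Wilcoxon, 45 min | Wilcoxon, 90 min |
|---|---|---|
| none | 67–69% | 64–69% |
| half | 47–61% | 46–53% |
| all | 10–55% | under 1% to 21% |

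A rank test of exact time to readiness in all patients has about 78%. That is a ceiling, since the trial sees readiness only at three times. When all ready patients leave, the mean score difference at 90 minutes shrinks from between −0.80 and −1.15 (all patients) to between −0.12 and −0.52 (those present). When half leave, it does not shrink: −0.99 to −1.15 among those present, against −0.81 to −1.13 in all. Power still falls there because fewer patients are scored.

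**6. No true effect.** In model A the tests reject in the favourable direction in about 2–3% of trials (nominal 2.5%). In model B, two-sided rejection among those present is 3.0–5.3% (nominal 5%). Neither shows false-positive inflation.

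**The case against.** A reader might infer that 4.9 prescribes separate t-tests or Wilcoxon tests of DASAIM at 45 and 90 minutes. It does not. The DASAIM sentence promises only a summary, and the test sentence is generic. A by-arm comparison of the scores is the natural reading, because that summary sentence also lists insufflation pressure and length of stay and the test for continuous variables follows directly. If the test does not cover DASAIM, outcome 4.2.4 has no clearly assigned between-arm analysis, and the same paragraph is needed.

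A reader might also infer that the plan rejects the readiness rule, or that it states a null of equal readiness among all randomised patients. Neither is in the documents. The categorical tests in 4.9 could be applied to readiness, although 4.9 does not say so. Applied only to patients still scored, they would carry the same selection.

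The strongest objection is to the size. No passage says that meeting the DASAIM rule triggers departure, and if nobody leaves early there is no selection. At 45 minutes, in model A, the score test is no worse than the proposed analysis when 25% or fewer of the ready patients leave. All of this stands. It limits how firmly the size can be stated. It does not supply the missing rule, and 6.2.5 itself provides for early discharge.

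**Conclusion.** The point holds as a conditional defect in the analysis of one secondary outcome. To the extent that patients leave before 45 or 90 minutes, the plan as naturally read compares slow recoverers rather than randomised groups. The comparison loses power and, when most ready patients leave, the difference is pulled toward zero. Under model A's assumptions the loss against a readiness analysis is about 20 points at 45 minutes if 75% of ready patients leave, and about 25 points at 90 minutes if 50% leave. These figures illustrate direction and scale and are not estimates for this trial. The 15-minute score, the primary outcome and the sample size are unaffected, and the simulations give no reason to fear false positives. The change is worth making before any by-arm data are seen.

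**What to change.** In section 4.9, make readiness by the 6.2.5 rule the analysed variable for outcome 4.2.4, in all randomised patients:

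- Code the first assessment at which the rule is met as 15, 45, 90 or not by 90 minutes.
- Count a patient discharged from the PACU after recovery, without an earlier qualifying score, as ready from the next scheduled assessment.
- Code a patient moved for another reason, such as transfer to ICU, as not ready.
- Compare arms with the Wilcoxon rank sum test already planned.
- Report the cumulative proportion ready at 15, 45 and 90 minutes, with all randomised patients as the denominator.
- Keep the raw 45- and 90-minute scores as description only, with the number scored in each arm.

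The cost is one paragraph and some data extraction. Section 6.1 already names PACU notes and a PACU survey as sources. No passage lists the time and reason for leaving as collected items, so both must be taken from those notes. Departure is also only a partial proxy for readiness, since a patient may leave or stay for logistical reasons.

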2.2 The adoption of continuous deep neuromuscular blockade combined with lower insufflation pressures during robotic prostatectomy will have the most significant effects for patients with multiple comorbidities, such as obesity, age greater than 65, history of congestive heart failure, chronic obstructive pulmonary disease, chronic renal insufficiency, diabetes mellitus, peripheral vascular disease and sarcopenia.

3. Objectives

3.1 Primary: To compare the effect of deep neuromuscular blockade with Sugammadex reversal versus moderate neuromuscular blockade with neostigmine reversal (standard of care) on postoperative shoulder pain.

3.2 Secondary: To assess the effect of deep neuromuscular blockade with Sugammadex reversal versus moderate neuromuscular blockade with neostigmine reversal on intraoperative insufflation pressures, perioperative recovery and morbidity for robotic prostatectomy.

4. Study Design

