4.8. Sample Size Justifications

For 99 patients undergoing laparoscopic hysterectomy, 28.6% of the DNMB group (IP 8mmHg) vs. 60% in the MNMB group (IP 12mmHg) experienced shoulder pain. (Madsen, et al., 2016)

Using the data from the aforementioned study, a sample size of 48 per group will enable the study 88% power to detect the decrease in the rate of postoperative shoulder pain from 60% for the control group to 28.6% for the group with deep Neuromuscular Blockade and Sugammadex, assuming a two-sided type I error rate of 0.05 using a two-group Chi-square test (nQuery Advisor 7.0). Postoperative shoulder pain is defined as any shoulder pain recorded before the discharge from PACU. We predict that the typically increased length of robotic surgery in combination with potentially lower insufflation pressures (6-7mmHg) may result in an even greater difference between the two groups. We want to factor in a 4% drop-out rate, therefore, we will enroll a total of 100 patients.

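### The logistic regression in Section 4.9 has no sparse-data remedy; if the comorbidities of Section 2.2 enter it jointly by ordinary maximum likelihood, the adjusted treatment log odds ratio is about 10–15% too large

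*Combined protocol and SAP*

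**What the plan says.** The combined protocol and SAP describes the adjusted analysis in one sentence of Section 4.9: "Logistic regression will be utilized to assess the effects of patient prognostic factors, comorbidities and treatment on postoperative shoulder pain and postoperative morbidity". It does not list the covariates, limit their number, say whether they enter together, name an estimator, or say what happens if a category is sparse.

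The only list of comorbidities is in the second hypothesis (Section 2.2, repeated in the synopsis): "obesity, age greater than 65, history of congestive heart failure, chronic obstructive pulmonary disease, chronic renal insufficiency, diabetes mellitus, peripheral vascular disease and sarcopenia". That is eight items. Section 4.5.1 admits only patients aged 65 or older, so the age item separates patients in their 66th year of life from everyone else and is nearly constant.

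Section 4.8 sizes the trial on an unadjusted comparison: "a sample size of 48 per group will enable the study 88% power to detect the decrease in the rate of postoperative shoulder pain", "assuming a two-sided type I error rate of 0.05 using a two-group Chi-square test". Section 4.9 separately plans chi-square or Fisher tests for categorical variables. The logistic model is therefore an additional analysis.

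**The concern.** Ordinary logistic regression by maximum likelihood is biased in small samples. With few events per parameter the coefficients drift away from zero, so a protective treatment looks more protective than it is. If every patient with a rare condition has the same outcome, the estimate for that condition is infinite.

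The model in Section 4.9 is the only planned adjusted estimate of the treatment effect on the primary outcome, and it is also meant to describe comorbidity effects. An exaggerated adjusted odds ratio could be reported beside the unadjusted result and read as the better estimate. Naming the covariates would not cure this: writing the eight items into the plan would leave both the bias and the sparse cells in place.

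**Working it through.** **Inputs from Section 4.8.** Shoulder pain 60% (control) and 28.6% (deep block); 48 per group; two-sided 0.05; chi-square test; 4% drop-out, 100 enrolled, 96 evaluable.

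**1. The plan's own figure.**
- Mean rate = (0.60 + 0.286)/2 = 0.443; difference = 0.314.
- Null SE = √(2 × 0.443 × 0.557/48) = 0.1014.
- Alternative SE = √((0.60 × 0.40 + 0.286 × 0.714)/48) = 0.0962.
- Power = Φ((0.314 − 1.96 × 0.1014)/0.0962) = Φ(1.198) = 88.5%, which agrees with the stated 88%.

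**2. Events per parameter.**
- Events = 48 × (0.60 + 0.286) = 42.5, with 53.5 non-events.
- Treatment plus seven usable comorbidities: 42.5/8 = 5.3.
- With the over-65 indicator: 42.5/9 = 4.7.
- With 12 parameters: 3.5. With 15 parameters: 2.8.
- At the colorectal rates quoted in the background (3.3% and 25.8%), events = 48 × 0.291 = 14, or 14/9 = 1.6 per parameter.

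**3. True treatment effect.** ln(0.286/0.714) − ln(0.60/0.40) = −0.915 − 0.405 = −1.32, an odds ratio of 0.267.

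**4. Bias, by simulation.** 96 patients, marginal rates fixed at 60% and 28.6%, 4,000 trials per scenario (Monte Carlo error of the relative bias 0.6–0.8%). All prevalences are assumptions. The middle set is obesity 35%, heart failure 5%, COPD 8%, renal insufficiency 10%, diabetes 20%, vascular disease 5%, sarcopenia 20%, over-65 95%. In the rows marked b = 0.5 the covariates affect the outcome, and bias is measured against the conditional log odds ratio, so it is not an effect of adjustment itself.

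| Model | True log OR | ML mean | ML bias | ML coverage | Firth bias |
|---|---|---|---|---|---|
| 9 parameters, null covariates | −1.320 | −1.496 | 13.3% | 93.7% | 1.8% |
| 9 parameters, b = 0.5 | −1.386 | −1.571 | 13.4% | 93.5% | 1.1% |
| 8 parameters (no age item), b = 0.5 | −1.383 | −1.552 | 12.3% | 93.6% | 1.1% |
| 12 parameters, b = 0.5 | −1.439 | −1.712 | 18.9% | 93.0% | 1.2% |
| 15 parameters, b = 0.5 | −1.489 | −1.892 | 27.1% | 90.4% | 2.4% |
| 4 parameters, b = 0.5 | −1.370 | −1.462 | 6.7% | 94.8% | 0.4% |

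The unadjusted estimate is only 2–3% too large. In the first row the bias is 0.176 against an SD of 0.531, a ratio of 0.33; the odds ratio at the mean estimate is 0.224 instead of 0.267. Across separate simulations with null covariates and 8 or 9 parameters, ML means ran from −1.45 to −1.52 (10–15%), mostly −1.48 to −1.52.

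**5. Infinite estimates.** For one null comorbidity of prevalence p, the chance that all carriers share one outcome is
(1 − 0.6p)^48 (1 − 0.286p)^48 + (1 − 0.4p)^48 (1 − 0.714p)^48 − 2(1 − p)^96.
- p = 2%: 0.425 + 0.341 − 0.288 = 48%.
- p = 5%: 0.116 + 0.066 − 0.015 = 17%.
- p = 10%: 0.0127 + 0.0040 − 0.0001 = 1.7%.

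At least one infinite estimate in the joint model:
- rarer conditions at 2–5%: 86% of trials;
- middle set: 45–47%, or 36% without the age item;
- all conditions at 10% or more: 4–7%.

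Over all simulations the ranges were about 30–86% with rarer conditions at 2–8%, and about 4–10% with all at 10% or more. In the first two sets the over-65 indicator alone was inestimable in 17–22% of trials.

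**The case against.** The strongest reply is that the model criticised is not written down. Section 4.9 does not mention maximum likelihood, a joint model or nine parameters, and the items in Section 2.2 are offered as examples of patients who may benefit most, not as a covariate list. A univariable analysis or a short adjusted model would also satisfy the sentence. This stands as a limit on the claim: the joint model is a reasonable inference, since maximum likelihood is the default and no other comorbidity list exists, but it is conditional. It does not remove the point, because a four-parameter maximum-likelihood model still shows about 7% bias.

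Stronger readings that a reader might infer are not supported:

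- **That the primary result is biased.** The powered comparison is an unadjusted chi-square test, which this leaves untouched.
- **That infinite odds ratios are to be expected.** That depends wholly on prevalences the documents do not give; with all conditions at 10% or more it is uncommon.
- **That the model seriously inflates type I error.** Simulated rates for treatment were mostly about 5.5–6.5% (7.3% at the highest), and a four-parameter model gave 6.1% (Wald) and 6.5% (likelihood ratio), so the excess is not clearly due to the larger model.
- **That this is the only look at comorbidities.** Section 4.3.2 lists an optional subgroup analysis, and Section 4.9 allows simple categorical tests.
- **That separate comorbidities must be dropped.** Firth estimation with all nine covariates already removes nearly all the bias.

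**Conclusion.** The concern holds in a conditional and modest form. If treatment and the Section 2.2 comorbidities are fitted jointly by ordinary maximum likelihood, the adjusted treatment log odds ratio is about 10–15% too large with 8 or 9 parameters, and 19–27% too large with 12 to 15. At 8 or 9 parameters the bias is about one third of a standard deviation and coverage stays near 94%, so it would seldom change a conclusion by itself.

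The result assumes the Section 4.8 event rates; lower rates would leave fewer events per parameter. The frequency of infinite comorbidity estimates cannot be fixed from the documents and should be quoted only with its prevalence range. No event rate is given for postoperative morbidity, so the size of the problem there cannot be computed.

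Severity is minor: it concerns the only adjusted treatment estimate, not the powered analysis.

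**What to change.** In Section 4.9, state that the logistic models will be fitted by Firth penalised likelihood with profile penalised-likelihood intervals. Use a short covariate list fixed before analysis, with age in years in place of the over-65 indicator. The estimator matters as well as the list: shortening to four parameters alone leaves about 7% bias, while Firth with the same 8 or 9 covariates leaves about 2% or less and gives finite estimates throughout.

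Replacing the separate comorbidities by a count is optional. If a count is used, obesity should not be in it while BMI is also a term.

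The cost is a few lines of text and standard software, with no new data or patients. The downside is that penalised estimates are slightly shrunken and need profile intervals instead of the more familiar Wald intervals.

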5.1. Sugammadex

5.1.1. Dosage Forms And Strengths: 200 mg/2 mL (100 mg/mL) in a single-dose vial for bolus injection and 500 mg/5 mL (100 mg/mL) in a single-dose vial for bolus injection.

5.1.2. Recommended Dose and Administration: 4 mg/Kg, intravenously as a single bolus injection.

